## Participant Flow:

Recruitment Details		The Trial recruitment period had a start date of July 22nd and ended on August 7th 2024. (A total of 17 days) All participant recruitment and interviews were conducted at the AbbyCare Clinic in Woodstock, GA.				Total (Not public)	
Pre-assignment Details		Arm/Group Title		Sham Device		Total (Not public)	
Arm/Group Description		IR REHAB Device		Participants will receive 6 treatment...			
Period Title: Overall Study							
Started		16		15		31	
Completed		16		13		29	
Not Completed		0		2		2	
Reason Not Completed							
Withdrawal by Subject		0		2		2	
[Not Public]		Not Completed =0		Total from all reasons =0			
[Not Public]		Total from all reasons =0		Total from all reasons =2			

U.S. National Library of Medicine | U.S. National Institutes of Health | U.S. Department of Health & Human Services

## Baseline Characteristics:

Arm/Group Title		IR REHAB Device		Sham Device		Total	
Arm/Group Description		Participants will receive 6 treatments of 15 minutes each with an active IR REHAB device over the period of three weeks.		Participants will receive 6 treatments of 15 minutes each with a disabled (sham) IR REHAB device over the period of three weeks.			
Overall Number of Baseline Participants							
▼ Baseline Analysis Population Description		16		13		29	
[Not specified]							
Age: Categorical Measure Type: Count of Participants	Number Analyzed	16 participants		13 participants		29 participants	
Unit of measure: participants							
≤18 years	0	0%		0	0%	0%	
Between 18 and 65 years	11	68.75%		12	92.31%	23	
≥65 years	5	31.25%		1	7.69%	6	
Sex: Female, Male Measure Type: Count of Participants	Number Analyzed	16 participants		13 participants		29 participants	
Unit of measure: participants							
Female	6	37.5%		6	46.15%	12	
Male	10	62.5%		7	53.85%	17	
Race/Ethnicity: Customized Measure Type: Count of Participants	Number Analyzed	16 participants		13 participants		29 participants	
Unit of measure: participants							
Race	White	13	81.25%	8	61.54%	21	
	Black	2	12.5%	4	30.77%	6	
	Hispanic	1	6.25%	0	0%	1	
	Other	0	0%	1	7.69%	1	
IR REHAB Clinical Trial Participants	Number Analyzed	16 participants		13 participants		29 participants	
Measure Type: Count of Participants							
Unit of measure: participants							
	16	100%		13	100%	29	
						100%	

U.S. National Library of Medicine | U.S. National Institutes of Health | U.S. Department of Health & Human Services

## Outcome Measures:

1. Primary Outcome	
Title:	Measured Change in the Participants Pain Levels
► Description:	Participants pain levels will be measured using a visual analog scale ...
	If reporting a score on a scale, please include the unabbreviated scale title, the minimum and maximum values, and whether higher scores mean a better or worse outcome.
Time Frame:	Participants will indicate their pain level before and after each of six therapy sessions over a period of three weeks
▼ Outcome Measure Data	✓
► Analysis Population Description	
Arm/Group Title	IR REHAB Device
► Arm/Group Description:	Participants will receive 6 treatment...
Overall Number of Participants Analyzed	Participants will receive 6 treatment...
Mean (95% Confidence Interval)	16
Unit of Measure: Score on a scale	61.46 (47.70 to 72.63)
Arm/Group Title	Sham Device
► Arm/Group Description:	Participants will receive 6 treatment...
Overall Number of Participants Analyzed	Participants will receive 6 treatment...
Mean (95% Confidence Interval)	13
Unit of Measure: Score on a scale	19.79 (4.89 to 37.34)

[figure not shown]
## Outcome Measures - continued:

Delete			
Statistical Analysis Overview	Comparison Group Selection	IR REHAB Device, Sham Device	
	Comments	Null Hypothesis: There is not a statistically significant difference in nociceptive musculoskeletal pain when using an IR REHAB device when compared with a sham (placebo) device as a therapy in an approved and standardized clinical protocol.	
	Type of Statistical Test	Superiority	
	Comments	It was calculated that 24 participants randomized 1:1 between 2 arms would have at least an 85% power to detect a difference in pain relief of 30 points as measured using a Visual Analog Device. The actual difference in the mean of the change in pain level, as measured using a Visual Analog Scale, between the two independent groups is 41.67. Results of the post trial calculation was a 95.7% power to detect the difference in pain relief using 29 randomized participants.	
Statistical Test of Hypothesis	P-Value	<0.01	
	Comments	The threshold is P-value <0.05 for statistical significance A bootstrap N=20,000 was used for all estimates	
	Method	t-test, 2 sided	
	Comments	[Not specified]	
Method of Estimation	Estimation Parameter	Mean Difference (Net)	
	Estimated Value	41.67	
	Confidence Interval	(2-Sided) 95% 20.15 to 61.67	
	Estimation Comments	[Not specified]	

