## **Analysis**

To examine the research question, independent sample *t*-tests using the statistical analysis program IBM SPSS ver.30 will be conducted on the data set. The data set will be comprised of comparative results from the two trial groups, the Care as Usual Study Group and the Sham (placebo effect) Study Group. The tests will be bootstrapped to a test size of N=20,000 for validation.

An independent samples *t*-test is the appropriate statistical test when the purpose of research is to assess if differences exist on a continuous (interval/ratio) dependent variable by a dichotomous (2 groups) independent variable. The continuous dependent variable to be tested is the change in pain level of the joint or body area treated during the clinical trial. Each participant will be asked to indicate on a standard 100mm Visual Analog Scale their pain levels before the first treatment and after each of the prescribed treatments. The difference between the initial pain level of a participant and the level of pain indicated after their sixth and final treatment will be statistically analyzed to determine if there is a significant difference between those in the Care As Usual Group and the Sham (placebo) Group.

The dichotomous independent variables for the data set is the change in pain level of each participant in the group treated with the invisa-RED Technology IR REHAB Low-level Laser Therapy (LLLT) device and the group treated using the sham (placebo) device as a therapy in the standardized clinical protocol. The assumptions of normality and homogeneity of variance will be assessed. Homogeneity of variance assumes that both groups have equal error variances and will be assessed using Levene's Test for the Equality of Error Variances. Each *t*-test will be two tailed with the probability of rejecting the null hypothesis when it is true set at  $p < 0.05$ . This ensures a 95% certainty that the differences did not occur by chance. Data produced by both groups will be the results of a clinical trial governed and conducted as a randomized single - blind study using an IRB approved clinical protocol.

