## Graphs Depicting Results - continued:

**Comparative Clinical Trial Results by Participant**

## Graphs Depicting Results - continued:

## Study Results

The “Clinical Trial to Establish the Safety and Efficacy of the IR REHAB Device When Used as an Adjunctive Therapy for Nociceptive Musculoskeletal Pain”

FDA Study NCT06393088, was designed to provide data with which to evaluate the efficacy and safety of the invisa-RED® IR REHAB Low-level Laser Therapy (LLLT) device as compared with a sham device when used for the adjunctive treatment of musculoskeletal pain. This single blind trial of two groups; one group treated as usual, the other treated using a sham device. At the conclusion of the trial; results from the two groups were statistically analyzed to determine the efficacy and safety of the invisa-RED® IR REHAB machine for the adjunctive treatment of nociceptive musculoskeletal pain.

The study was designed as a superiority trial with a null hypotheses which asserted, in the population where the sample was obtained there was no difference between the intervention (IR REHAB) and placebo (Sham Device) groups in the mean change in the primary outcome variable:

However, the results of a bootstrapped (N=20,000) independent samples 2 sided t-test revealed:

An estimated mean difference (net value) of 41.67% greater reduction in participant's pain level when using the invisa-RED® IR REHAB as compared to the Sham Device this with a 95% confidence level from 20.15% to 61.67% and a two tailed P value < 0.01.

Therefore by conventional criteria the results are considered to be statistically significant for the trial's primary outcome variable, disproving the null hypotheses and affirming the alternative hypotheses that there exists an interventional superiority of the invisa-RED® IR REHAB therapy over the Sham Device (placebo).

Additionally and of great significance, there were zero adverse effects or mortality reported during or after the the clinical trial.

Three additional bootstrapped analysis (N=20,000) of the data were conducted:

- 1) An independent samples effect size analysis was conducted using Cohen's d and resulted in a value of 1.44, which by convention indicates a large effect size for the invisa-RED® IR REHAB over a placebo.

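### The 95.7% post-trial power is power at the observed effect and does not support the design; its count of 29 randomized is the analysed count, and the safety denominators and the unit of 41.67 conflict between sections

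*Combined protocol and SAP*

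**What the plan says.** Three statements on power and effect stand together in Outcome Measures - continued, in the comments on the type of test.

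- Planning: "It was calculated that 24 participants randomized 1:1 between 2 arms would have at least an 85% power" for a difference of 30 points. No SD is given.
- Observed effect: the difference in mean change, "as measured using a Visual Analog Scale, between the two independent groups is 41.67".
- Post-trial power: "Results of the post trial calculation was a 95.7% power to detect the difference in pain relief using 29 randomized participants". The sentence names no SD and does not repeat a difference.

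Study Results adds a Cohen's d that "resulted in a value of 1.44".

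On counts, Participant Flow lists 16 active and 15 sham started (31), 16 and 13 completed (29), and two withdrawals by subject, both sham. Outcome Measures analyses 16 and 13. Reporting Groups describes the 13 sham completers as the randomly selected control group. Adverse Effects Overview uses 18 active and 13 sham as the numbers at risk.

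On units, the Analysis section has participants "indicate on a standard 100mm Visual Analog Scale their pain levels before the first treatment" and analyses the change from that value. Outcome Measures labels the arm means "Unit of Measure: Score on a scale". Study Results instead reports "An estimated mean difference (net value) of 41.67% greater reduction" with a "95% confidence level from 20.15% to 61.67" percent.

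**The concern.** A power of 95.7% printed shortly after a claim of at least 85% power for 30 points invites the reader to think that the trial ended with better power for its design difference than planned. If the 95.7% was calculated at the observed effect, that impression is false: power at the observed effect is a function of the p-value and the sample size, so it carries no information beyond the test and its confidence interval.

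Three reporting faults affect how the result is read. Calling 29 the randomized number obscures that the analysis is of completers and that every loss was in one arm. Safety denominators that exceed the number started on the active device cannot stand beside the flow table. And a headline effect given as a scale score in one section and as a percentage in another cannot safely be compared with a 30-point planning difference.

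**Working it through.** **Inputs.** Two-sided t-test at 0.05 and difference 41.67 (Outcome Measures - continued); d = 1.44 (Study Results); 16 and 13 analysed (Outcome Measures); design difference 30 points (Outcome Measures - continued). The arm means agree with the difference: 61.46 − 19.79 = 41.67.

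**1. Reproducing the 95.7%.** Power of the two-sample t-test comes from the noncentral t distribution with n1 + n2 − 2 degrees of freedom and noncentrality d / √(1/n1 + 1/n2).

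- √(1/16 + 1/13) = 0.3734
- Noncentrality = 1.44 / 0.3734 = 3.857
- Degrees of freedom = 27, critical value 2.052
- Power = 96.0%

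This is 0.3 points above the printed figure. A small change of convention covers the gap: 14 per arm with the same d gives 95.6%. The observed effect therefore accounts for the 95.7%.

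**2. Why this adds nothing.** The noncentrality of 3.857 is simply the t statistic implied by d and the arm sizes. On 27 degrees of freedom it corresponds to p of about 0.0006, in line with the printed p < 0.01. The power figure is that same statistic on another scale.

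**3. Power for the design difference, if 41.67 is in VAS points.**

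- Implied SD = 41.67 / 1.44 = 28.9
- Standardised design difference = 30 / 28.9 = 1.037
- Noncentrality = 1.037 / 0.3734 = 2.776
- Power with 16 and 13 = 76.3%

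For 95.7% to apply to 30 points with 16 and 13, d would have to be 1.425, so the SD would be 30 / 1.425 = 21.1. That is well below 28.9.

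**4. Counts.**

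| Source | Active | Sham | Total |
|---|---|---|---|
| Participant Flow, started | 16 | 15 | 31 |
| Participant Flow, completed | 16 | 13 | 29 |
| Outcome Measures, analysed | 16 | 13 | 29 |
| Adverse Effects Overview, at risk | 18 | 13 | 31 |

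The 29 matches completed and analysed, not started. The at-risk total agrees with the number started, but the split does not: 18 exceeds the 16 who started on the active device. The split would arise if the two sham withdrawals had been added to the active arm (16 + 2 = 18), but the documents do not say so.

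**5. Unit.** The point estimate and both interval limits (41.67, 20.15, 61.67) are the same numbers in Outcome Measures - continued and in Study Results, without a percent sign in the first and with one in the second. Percent of the 100 mm scale would be numerically the same as points. Percent of each participant's baseline would be a different quantity, and step 3 would then not apply.

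**The case against.** The strongest reply is that the power sentence is not obscure. The sentence before it calls 41.67 the actual difference, so the plain reading of the difference to be detected is 41.67, and with the printed d the figure can be recovered. That stands. It would be wrong to say that the difference is missing or that 95.7% is an arithmetic error; the small gap from 96.0% has no evidential weight. What remains is that no SD is printed and that the figure is not labelled as power at the observed effect.

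Second, all 29 participants were indeed randomized, Participant Flow openly shows 31 started, and using 16 and 15 moves the observed-effect power only from 96.0% to 97.2%. This is fair on size. But the phrase gives the analysed count where a reader expects the randomized count, and Reporting Groups does the same for the sham arm.

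Third, the unit may be explained in text not visible here, since the outcome description is cut short and the graphs are not shown. That could settle what was meant, but it would not remove the percent signs in Study Results.

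A reader might infer more: that the trial was underpowered, or that the 85% with 24 participants is wrong. The documents support neither. No planning SD is printed, so the 85% cannot be refuted; the 76% rests on an SD taken from the results and on the points reading.

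**Conclusion.** The point holds at minor severity. The 95.7% is best read as power at the observed difference (96.0% on recalculation) and gives no support to the 30-point design. Power for 30 points with 16 and 13 would be about 76%, assuming that 41.67 is in VAS points and that 28.9 is the SD.

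The count of 29 is the completed and analysed number out of 31 started. This takes started to mean randomized, which is reasonable because the flow table counts it by arm. The at-risk split of 18 and 13 contradicts the flow table's 16 and 15 whatever view is taken of the power. The unit of the headline estimate is inconsistent between Outcome Measures and Study Results.

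None of this alters the printed p-value, and neither Study Results nor the conclusions section cites the 95.7%.

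**What to change.** 1. In Outcome Measures - continued, delete the 95.7% and rely on the confidence interval, or label it as power at the observed effect and state the difference and SD used.
2. Replace the count in that sentence with 29 analysed of 31 started (16 active, 15 sham), with two sham withdrawals. Align Reporting Groups with this.
3. Reconcile the at-risk denominators in Adverse Effects Overview with Participant Flow.
4. State one unit for 41.67 and its interval (20.15 to 61.67) in Outcome Measures, its continuation and Study Results: VAS points, percent of the scale, or percent of baseline.

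The cost is text only, with no new participants and no re-analysis. The sponsor gives up, or relabels, one favourable figure.

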## **Reporting Groups**

The first was the **IR REHAB Group** which was a randomly selected group of sixteen (16) participants who received treatment per the prescribed trial protocol using a fully functional invisa-RED Technology IR REHAB device. Treatment protocol is as follows: Participants will undergo six (6) therapy sessions of 15 minutes each over a three week period. Power settings will be based on the participants Fitzpatrick Scale skin type. For skin types i and ii a power setting of 7 was used, for skin types iii and iv a power setting of 6, for skin types v and vi a power setting of 4 was employed. Each participant randomly assigned to the IR REHAB group underwent six therapy sessions over three weeks using a fully functional invisa-RED Technology IR REHAB device.

The second group was the **Sham Group** which was a control group of thirteen (13) randomly selected participants who received a placebo treatment per the prescribed trial protocol using a non functional IR REHAB device. (The sham device was disabled and delivered no Low-level Laser Light energy during therapy but appeared to be fully functioning and powered-up.) Treatment protocol was as follows: Participants underwent six (6) therapy sessions of 15 minutes each over a three week period. Power settings were input based on the participants Fitzpatrick Scale skin type as per usual. For skin types i and ii a power setting of 7 was input, for skin types iii and iv a power setting of 6, for skin types v and vi a power setting of 4 was utilized. Each participant randomly assigned to the "Sham Group" underwent six therapy sessions over three weeks using the sham (non functioning invisa-RED Technology IR REHAB) device.

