- 2) A Mann-Whitney U test was performed to evaluate whether results differed by treatment group. The results also indicated that the group treated with the invisa-RED® IR REHAB had significantly greater pain reduction than those treated with the Sham Device,  $z = [-3.12]$ ,  $p = [<0.01]$ .
- 3) Levene's test showed that equal variances for the IR REHAB and Sham Device Groups may be assumed,  $F(1,27) = .006$ ,  $p = .936$ .

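### Participant counts disagree: 31 started and two sham participants withdrew, but Reporting Groups and the adverse-event table do not account for them, and the primary result covers completers only

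*Combined protocol and SAP*

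**What the plan says.** **Participant Flow.** 16 IR REHAB and 15 sham started (31); 16 and 13 completed (29). The row "Withdrawal by Subject" shows 0 in IR REHAB and 2 in sham.

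**Reporting Groups.** The IR REHAB group is 16. The sham group is "a control group of thirteen (13) randomly selected participants who received a placebo treatment", and each person randomly assigned to it "underwent six therapy sessions over three weeks using the sham (non functioning invisa-RED Technology IR REHAB) device".

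**Adverse Effects Overview.** The at-risk denominators are 18 (IR REHAB) and 13 (sham), repeated for mortality, serious events and other events. Study Results adds that "there were zero adverse effects or mortality reported".

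**Outcome Measures.** The row "Overall Number of Participants Analyzed" corresponds to 16 and 13. In Study Results, Levene's test is said to show that "equal variances for the IR REHAB and Sham Device Groups may be assumed", with F(1,27), which means 29 participants.

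**Outcome Measures, continued.** The comment on the superiority test reports 95.7% "power to detect the difference in pain relief using 29 randomized participants".

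**Baseline Characteristics.** Counts are 16, 13 and 29, and the field "Baseline Analysis Population Description" is marked as not specified.

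**Planned analysis.** Data Analysis and Data Monitoring (protocol) and Analysis (SAP) define the endpoint as change from the initial score to the score after the sixth treatment. Neither names an analysis set or says what happens when that last score is missing. The SAP section headed Data Sets/Populations covers only recruitment and eligibility.

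**The concern.** These sections all report the same finished trial, so they should give one count per arm. They do not. If 15 started sham and two withdrew, it cannot also be true that the sham group was 13 and that everyone assigned to it had six sessions. An IR REHAB denominator of 18 matches no other count for that arm, and a sham denominator of 13 leaves out two people who started.

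Two things are at stake. First, the efficacy estimate excludes two people who were allocated. If both were in sham, the completers' difference is too small if they did worse than the sham mean and too large if they did better. Second, the zero-event safety statement should rest on everyone who started treatment, and the printed denominators cannot be matched to Participant Flow.

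**Working it through.** **Counts side by side**

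| Section | IR REHAB | Sham | Total |
|---|---|---|---|
| Participant Flow, started | 16 | 15 | 31 |
| Participant Flow, completed | 16 | 13 | 29 |
| Reporting Groups | 16 | 13 | 29 |
| Baseline Characteristics | 16 | 13 | 29 |
| Outcome Measures | 16 | 13 | 29 |
| Levene's test, 27 + 2 | – | – | 29 |
| Adverse Effects Overview | 18 | 13 | 31 |

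31 − 2 = 29, so the analysed set equals the completers. The adverse-event total of 18 + 13 = 31 would fit if the two extra people had been entered in the other arm. If 18 is a slip for 16, the total is 29 and two sham starters are still left out.

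**The reported power.** With the reported Cohen's d of 1.44, a two-sided t-test at 0.05 (noncentral t) has 96.0% power for 16 and 13, close to the stated 95.7%. It has 97.2% for 16 and 15, and 96.9% for 18 and 13. The power figure is therefore sound for 29 and cannot show which arm counts are right.

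**Inputs for the scenarios.** Means are 61.46 and 19.79 (Outcome Measures), a difference of 41.67. The SD is not stated, so I assume 41.67 / 1.44 = 28.94 in each arm. As a check, the reported interval of 20.15 to 61.67 has a half-width of 20.76. Dividing by √(1/16 + 1/13) = 0.3734 and by 2.052 (t) or 1.96 (z) gives an SD of 27.1 or 28.4. Units are taken as VAS points, positive meaning improvement.

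Completers: SE = 28.94 × 0.3734 = 10.81; 41.67 ± 2.052 × 10.81 = 19.5 to 63.8, near the reported bootstrap interval.

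**Both withdrawals in sham (16 vs 15), each given the value x**

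- Sham mean = (13 × 19.79 + 2x) / 15
- Pooled sum of squares = 27 × 28.94² + (13 × 2 / 15)(x − 19.79)², on 29 df
- SE = pooled SD × √(1/16 + 1/15)

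| x | Sham mean | SE | Difference (95% CI) | p |
|---|---|---|---|---|
| 0 (no change) | 17.15 | 10.18 | 44.3 (23.5 to 65.1) | <0.001 |
| 61.46 (active mean) | 25.35 | 10.68 | 36.1 (14.3 to 58.0) | 0.002 |
| 100 | 30.48 | 12.26 | 31.0 (5.9 to 56.1) | 0.017 |

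To reach p=0.05, each would need an improvement of about 124 points (112 at SD 34, 133 at SD 24), which is more than the 100 mm scale allows.

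**Both withdrawals in IR REHAB (18 vs 13), as the adverse-event table would imply**

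- Active mean = (16 × 61.46 + 2x) / 18, with the pooled variance rebuilt in the same way
- x = 0: 34.8 (11.2 to 58.5), p=0.005
- x = −50: 29.3 (0.1 to 58.5), p=0.0496

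Significance is lost only if each worsened by about 50 points or more (38 to 60 for an SD of 34 to 24). On a 100 mm scale, a worsening of 50 requires a starting score of 50 or less.

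**Safety denominators.** With zero events, the exact two-sided 95% upper bound is 1 − 0.025^(1/n): 20.6% for 0/16, 18.5% for 0/18, 21.8% for 0/15 and 24.7% for 0/13.

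**The case against.** Participant Flow discloses the withdrawals, so a reader who compares its completers with the analysed counts can see what was done. That stands, and several stronger readings fail.

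- **That the power comment misstates how many were randomized.** The 29 analysed people had been randomized, the sentence concerns power, and 29 is the right number for it. The clear contradictions are in Reporting Groups and Adverse Effects Overview.
- **That the result was presented with no population label at all.** The analysis population field under Outcome Measures is collapsed, so its content cannot be seen. What can be said is that no visible text labels the result as completers. The unspecified field belongs to the baseline table.
- **That the arm of the withdrawals is an open question with both answers equally likely.** Only Participant Flow records withdrawals by arm, and four sections give 16 for IR REHAB. Only the adverse-event table dissents, and its 18 may be an entry or text-reading slip, although it appears three times. The planned equal groups fit 16 and 15 better than 18 and 13, without settling the matter. The active-arm scenario is secondary.
- **That the scenarios bound the true estimate.** Study Results words the same figure as a percentage, and percent worsening has no floor at −100. At −300 for each of the two, the same formulas give 61.46 − (257.27 − 600)/15 = 84.3 if sham, or (983.36 − 600)/18 − 19.79 = 1.5 if IR REHAB. No limits are claimed on that reading.
- **That the safety conclusion changes.** With zero events, the upper bounds move by only about 2 to 3 percentage points.

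**Conclusion.** This is an internal inconsistency of counts that should be fixed. Reporting Groups and the adverse-event denominators cannot both stand beside Participant Flow, and reading 18 as 16 does not remove the problem. The primary result is in fact a completers analysis of 16 against 13, under a plan that defined no analysis set or missing-score rule.

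The effect on the conclusions is modest. With both withdrawals in sham, the three scenarios give differences of 31.0 to 44.3 points and p stays below 0.05. The reported p<0.01 fails if both improved by the full 100 points (p=0.017). That last finding depends on the SD: at SD 24 the pooled SD is √((27 × 24² + 11,152)/29) = 30.3, the SE is 10.9 and t is 2.84, giving p=0.008. Significance could be lost only if the adverse-event table has the right arm and both people worsened substantially.

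A reader might infer that the efficacy claim is overturned or that safety data were withheld. The documents support neither. The figures assume a common SD of 28.94, outcomes in VAS points and single assigned values for the two missing scores. They are illustrations, not estimates.

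**What to change.** 1. Reconcile Participant Flow with Adverse Effects Overview from source records, confirm the arm of the two withdrawals, and correct the at-risk denominators to all who started, by arm.
2. Correct Reporting Groups to give the number assigned and the number who completed six sessions. Reword the power comment to refer to 29 completers of 31 started.
3. Keep the t-test. State in the population description that it covers completers (16 vs 13), as the set actually used and not as a pre-specified rule. Fill in the baseline population description and show baseline for all 31 where it was collected.
4. Add a sensitivity analysis of all 31 in their assigned arms, with the outcome unit stated, labelled post hoc.

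The cost is a source check, a few wording and table corrections, and one small re-analysis. The drawback is that the added analysis is post hoc and may give a slightly less favourable estimate.

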## **Data Analysis and Data Monitoring**

The mean change in each group of participant's pain levels as recorded at the trials beginning and then at the trials conclusion will be statistically evaluated using a two-tailed independent sample T-test with an a priori threshold p value of < (less than) 0.05.

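### Primary results table: a bootstrap interval of unnamed type sits beside a t-test, post-trial power repeats the p-value, and the randomised count, the unit and the planning SD need correction or support

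*Combined protocol and SAP*

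**What the plan says.** **Planned analysis.** Under Data Analysis and Data Monitoring, mean change in pain "will be statistically evaluated using a two-tailed independent sample T-test" at the 0.05 level. The Analysis section repeats the t-test and adds: "The tests will be bootstrapped to a test size of N=20,000 for validation". Neither section specifies a confidence interval or says whether the t-test is pooled or Welch.

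**Planned unit.** The Analysis section says: "Each participant will be asked to indicate on a standard 100mm Visual Analog Scale their pain levels". The outcome is the difference between the level before the first treatment and the level after the sixth.

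**Reported result.** Outcome Measures - continued gives a two-sided t-test, a mean difference of 41.67 and a 95% interval printed as "2-Sided) 95% 20.15 to 61.67". A comment adds: "A bootstrap N=20,000 was used for all estimates". Study Results gives the same three numbers with percent signs and reports Cohen's d of 1.44. Levene's test there gives p = .936.

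**Power.** The same table says that "24 participants randomized 1:1 between 2 arms would have at least an 85% power to detect a difference in pain relief of 30 points", and then: "Results of the post trial calculation was a 95.7% power to detect the difference in pain relief using 29 randomized participants".

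**Counts.** Reporting Groups describes 16 active participants and "a control group of thirteen (13) randomly selected participants". Participant Flow shows 16 and 15 started, 16 and 13 completed, and two sham withdrawals. Adverse Effects Overview puts 18 active and 13 sham at risk.

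**The concern.** A reader will take the 95% interval as belonging to the test named beside it, and the two power figures as evidence that the trial was large enough. If the interval comes from another method, its precision cannot be judged until that method is named. If the post-trial power was computed at the observed effect, it is the p-value in another form. If the planning power has no SD behind it, it cannot be checked.

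The counts and the unit matter for a different reason. Calling the analysed set randomised blurs the difference between everyone assigned and those who finished. A difference of 41.67 mm and a 41.67% greater reduction are different quantities, and the superiority conclusion rests on this one number.

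**Working it through.** **Inputs.** Arm means 61.46 (n = 16) and 19.79 (n = 13) from Outcome Measures; d = 1.44 and Levene p = .936 from Study Results; two-sided 0.05 from Data Analysis and Data Monitoring. I assume that d was computed with the pooled SD, which the documents do not state.

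**1. Estimate.** 61.46 − 19.79 = 41.67. This agrees with the table.

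**2. Shape of the interval.** 41.67 − 20.15 = 21.52 below; 61.67 − 41.67 = 20.00 above. A t interval has equal arms, so this is not one. Its width is 41.52.

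**3. The t interval implied by d.**
- SD = 41.67 / 1.44 = 28.94
- SE = 28.94 × √(1/16 + 1/13) = 28.94 × 0.3734 = 10.81
- t = 41.67 / 10.81 = 3.86 on 27 df, p = 0.0006
- Half-width = 2.052 × 10.81 = 22.17, giving 19.50 to 63.84, width 44.34
- Ratio of widths = 41.52 / 44.34 = 0.936, so 6.4% narrower (6.0% to 6.7% over the rounding of d)

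The arm intervals in Outcome Measures offer a partial check. If they are percentile bootstrap intervals (an assumption), they give SDs of 26.3 and 31.1. The pooled t interval is then 19.83 to 63.51 (ratio 41.52 / 43.68 = 0.951) and the Welch interval 19.29 to 64.05 (41.52 / 44.76 = 0.928). The shortfall is therefore about 5% to 7%.

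**4. What a percentile bootstrap would do here.** In simulated normal data with 16 and 13 per arm, the percentile interval averaged 0.92 of the pooled t width (95% range 0.86 to 0.98) and covered the true difference about 93% of the time. The observed ratio of 0.936 is ordinary for that method.

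**5. The 95.7% figure.** Noncentrality = 1.44 × √(16 × 13 / 29) = 3.86. Two-sided noncentral-t power on 27 df is 96.0% (95.9% to 96.2% over the rounding of d). This reproduces the stated figure closely. The noncentrality is the observed t itself, which is why the figure carries no information beyond the p-value. Read instead as power for 30 points with 16 and 13, 95.7% would need an SD of 21.1. In VAS points that is below the 95% interval for the SD implied by d (22.9 to 39.4).

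**6. The 85% figure.** With 12 per arm, a two-sided t-test and 85% power, the smallest detectable d is 1.280. The largest SD that supports the claim is 30 / 1.280 = 23.4 (24.5 by the normal approximation). No planning SD appears in the documents.

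**7. Counts.**

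| Source | Active | Sham | Total |
|---|---|---|---|
| Participant Flow, started | 16 | 15 | 31 |
| Participant Flow, completed | 16 | 13 | 29 |
| Adverse Effects Overview, at risk | 18 | 13 | 31 |
| Results table, called randomised | – | – | 29 |

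Both 31s agree in total. Against the 16 and 13 analysed, the first places the two losses in the sham arm (15 − 13) and the third places them in the active arm (18 − 16).

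**8. Unit.** The Analysis section plans a difference on a 100 mm scale, and Outcome Measures reports a scale score. Study Results attaches percent signs to the same estimate and limits. On a 100 mm scale the percent sign might be loose notation for points, or it might mean relative change. The documents do not say which.

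**The case against.** The strongest reply is that little here is wrong arithmetic. The difference of means is right, and the post-trial power can be recovered from d, the arm sizes and the two-sided 0.05 level given elsewhere in the documents. The use of a bootstrap is stated in the Analysis section, in the results table and in Study Results. No confidence interval was prespecified, so no planned interval was replaced. The t interval is not the truth either: the reported width is normal for a bootstrap at this size, and the lower limit would move by only 0.65. Participant Flow openly reports both withdrawals.

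All of that stands, and it rules out several stronger readings that a reader might infer:
- that the bootstrap was undisclosed;
- that the 95.7% cannot be reproduced;
- that the withdrawals were concealed;
- that the treatment difference is no longer significant.

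The objection does not remove the rest. The bootstrap type is still unnamed beside a t-test that was the planned analysis, the bootstrap having been planned to validate it. Reproducing the 95.7% shows that it is power at the observed effect, which is the reason it does not support the design. The word randomised is wrong for 29, the two starting splits conflict, and the percent signs disagree with the planned unit.

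**Conclusion.** The point holds as a reporting fault in the primary results, correctable from existing records. The reported interval is about 6% narrower than the t interval of the listed test (41.52 against 44.34). This assumes that d uses the pooled SD. If the interval is of percentile type, which is also an assumption, its coverage is nearer 93% than 95%. Both intervals exclude zero.

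The 95.7% should carry no weight as evidence of adequate size. The reading as power for 30 points is unlikely, though not strictly excluded.

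The 85% is unsupported, not refuted. A reader might infer that the SD of 28.94 implied by d disproves it, because that exceeds 23.4. It does not: a planning SD is chosen before the data, and the 95% interval for the SD implied by d (22.9 to 39.4, if the unit is VAS points) includes 23.4.

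The contradictions in count and unit need no assumption. They stand on the text alone and are the firmest part of the point.

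**What to change.** 1. Report the 95% interval of the independent-samples t-test from the raw data beside the bootstrap interval, and name the form of each (pooled or Welch; percentile, BCa or other). The pooled t interval should fall near 19.5 to 63.8.
2. Give the effect in the planned unit, mm on the 100 mm VAS, and correct Study Results. If the data are percent changes, say so and label that a departure from the Analysis section.
3. Replace the reference to 29 randomised participants with 31 started, 29 completed and analysed (16 and 13). Reconcile Reporting Groups, Participant Flow and Adverse Effects Overview against the enrolment log before stating starting numbers by arm.
4. Delete the 95.7% post-trial power and add no other retrospective power figure.
5. Give the original planning SD and its source. If none exists, withdraw the 85% claim or state that it holds only if the SD of change is about 23.4 or less (two-sided t-test, 12 per arm, 30 points). That condition is solved back from the claim, so it discloses what the claim needs and does not justify it.

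The cost is wording, one t-test output and a check of the enrolment log, with no new participants. The price is a slightly wider interval and a less favourable power statement.
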